The proposed research uses a cluster randomized controlled trial design to evaluate the effectiveness of TXTXT intervention on adherence and viral load suppression at 3 months post intervention initiation. A total of 12 clinic sites in the Midwest will be randomly assigned to either a 3- month observation period (i.e., comparison arm) or a 3-month intervention period (i.e., intervention arm). At the 3-month mark, sites randomized to the intervention arm will continue with the intervention for an additional 3 months, and sites initially assigned to the comparison arm will switch to the intervention for the 3 months. We will assess initial impact of the intervention by comparing the primary outcomes (i.e., ART adherence and viral load suppression) of the intervention arm to the comparison arm at 3-months post initiation of the intervention. This timepoint (3 months post baseline) was selected based on the findings of the randomized control trial used to establish efficacy of TXTXT.¹⁸ The study will also compare pre-post differences in adherence and viral load suppression for participants in the comparison arm at 6 months post baseline. Secondary outcomes of retention in HIV care and sustained impact of the intervention will be evaluated at 12 months post-baseline. At 3 months, 6 months, and 12 months post baseline, electronic medical record (EMR) data from participating clinics will be used to determine viral load and retention in care measures.

METHODS

Audience and Stakeholder Participation

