MATEC affiliated clinics in the Midwest region are eligible to participate in Aim 1 if meeting these criteria: (1) Clinic must have at minimum 40 current patients who are: racial/ethnic minority AND have a 'detectable' viral load AND are aged 16-35 years; (2) clinic must be willing to commit at least one staff person as lead for registering clients to receive the intervention, completing consent, and administering research surveys; (3) clinic must be willing to provide deidentified individual-level data for registered TXTXT participants, including viral load, retention in care (dates of clinic visits) at least twice per year; (4) clinic must not be using a competing medication reminder text messaging system; (5) clinic must be willing and able to rely on Lurie IRB. Once sites sign a memorandum of commitment, the study coordinator will schedule a conference call to conduct a standard of care questionnaire (Appendix K). The standard of care questionnaire will document existing clinic approaches to support adherence as well as any ancillary services (e.g., transportation assistance). This information will form a descriptive profile for each clinic.

Study Inclusion

For inclusion in the TXTXT intervention individuals must meet the following criteria: 1) diagnosed with HIV-infection and on ART regimen for at least one month (not new to ART); 2) aged 16-35 years; 3) have a viral load ≥ 200 c/mL and/or report poor adherence (<90% of pills taken in the last 30 days); 4) able to receive text messages; 5) provide informed consent for research component; and 6) are a patient of a participating clinic

Study Exclusion

Exclusion criteria includes: 1) those who are unable to give informed consent 2) those who are participating in other studies that impact primary and secondary outcomes.

Procedures for Recruitment and Informed Consent

Aim 1: Youth living with HIV (aged 16-35 years) who meet study inclusion criteria will be recruited by study staff from participating clinics. The EMR will identify potentially eligible patients who will be invited to complete further study screening and enrollment.

We will ask each clinic to construct a list of eligible patients and carefully track outreach, screening, and enrollment on an enrollment log provided. Clinics may enroll up to 50 participants (to account for 20% attrition, final sample of 40 participants per clinic).

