baseline	50 participants at each clinic	Participants at intervention clinics receive TXTXT	EMR data Baseline survey
		Participants at comparison clinics do not receive TXTXT (i.e., standard of care)	
3 months	50 participants at each clinic	Participants at intervention clinics continue with TXTXT	3-month survey
6 months	50 participants at each clinic	Participants at comparison clinics begin TXTXT TXTXT stops for all participants	EMR data 6-month survey
12 months	50 participants at each clinic		EMR data

Sampling

We will ask each clinic to construct a list of potentially eligible patients and carefully track outreach, screening, and enrollment on an enrollment log provided. Participants (N=600, n=50 per each clinic site) will be enrolled.

The list of potentially eligible patients will be constructed from available EMR data and will be queried based on: (1) diagnosed with HIV; (2) age range (16-35 years); (3) most recent viral load obtained in past 12 months. If potential participants meet the first two criteria, they will be evaluated based on (#3) viral load data. The following scenarios are possible: 1) potential participant is virally suppressed; 2) potential participant is viremic (>200 copies/mL); 3) potential participant does not have viral load data available. Patients who are viremic and meet criteria 1-3 (HIV status, age) will be considered eligible for study inclusion and will be called by clinic staff to confirm eligibility and assess interest. Patients who meet criteria 1 and 2 and are virally suppressed or missing viral load data will be contacted to assess eligibility - specifically, those who are virally suppressed will be queried about medication adherence (if <90% of pills taken in the past 30 days); for those who are missing viral load data they will be asked if they are willing to re-engage in HIV care and have labs drawn prior to enrollment (if so, they will follow steps outlined above for those with viral load

STUDY DESIGN AND DATA ANALYSIS

(VL) data). The list and eligibility assessment will be documented and reviewed on a weekly basis with individual sites to ensure timely enrollment into the study.

Data Analysis Plan and Variables

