In order to assess feasibility, acceptability and satisfaction of the intervention we will use descriptive statistics using a combination of objective (e.g., rates of participation, intervention completion) and subjective measures (e.g., reported satisfaction, acceptability). In order to characterize adherence and retention in care throughout the course of the study, Kaplan-Meier survival curves will be used to measure time to adherence and retention, and Cox proportional hazard ratios will be used to assess whether individual-level factors are associated with shorter mean time to outcome. To measure reach of the intended participants, we will compare the study sample to those available in the sampling frame (proportion of those enrolled to those eligible). To measure adoption of clinic partners, we will evaluate the number of clinic partners who propose to continue with text messaging as adherence support post study (proportion of clinics who propose to continue TXTXT post study to total clinics). Satisfaction and acceptability will be measured by standard quantitative scales, summary total scores will be evaluated to determine whether or not ≥90% ratings were achieved.

Outcome definitions

Medication adherence: greater than or equal to 90% on self-reported visual analog scaler (non-adherence categorized at less than 90%)

Retention in care³³: two visits 90 days apart in the past year will be considered retained in HIV care

Viral suppression³⁴: VL < 200 copies/mL will be considered virally suppressed

Sample size, power calculation, and clinic scale up

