Other language, if "other", specify _____ (*Check ineligible and continue*)

7. Do you have a cell phone that can send and receive text messages?

Yes

No (*Check ineligible and continue*)

Ineligible

RECRUITER INITIALS: _____

SCREENING DATE: _____

Month

Day

Year

8. How often would you say you use your cell phone for sending or receiving text messages?

Never (*Check ineligible and continue*)

Ineligibl

1-2 times per week

3-5 times per

week Almost

every day Every
day

Several times a day

9. Have you ever been told by a doctor or other health care provider that you have HIV infection or have AIDS?

Yes

Ineligible

No (*Check ineligible and go to ineligible script*)

10. Have you ever taken antiretroviral medications or HIV

medications? Yes

Ineligible

No (*Check ineligible and go to ineligible script*)

11. Can you tell me when you started taking antiretroviral medications or HIV medications?

≤ 1 month ago (*Check ineligible and
continue*)

Ineligibl

but ≤ 6 months ago

but ≤ 24 months ago

24 months ago

12. Are you currently participating in any other research studies or programs about HIV treatment or medication adherence (support for taking your HIV medications)?

Yes (*Check ineligible and go to ineligible script*)

Ineligible

No

13. I need to know how you are doing with taking your HIV medications. Remember that this is a study for people who are having trouble taking their meds. Please answer as honestly as you can.

1. How many medication doses would you say you missed in the past 7 days? _____ doses

2. How many medication doses would you say you missed last month?

If a) is 1 or less AND b) is less than 3, check ineligible

Ineligible

Questions 14-18 are for the interviewer only.
**DO NOT ASK THESE QUESTIONS OF THE
PARTICIPANT.**

RECRUITER INITIALS: _____ SCREENING DATE: _____
Month Day Year

3. Does the volunteer appear to speak and understand English or Spanish?
 Yes
 No (*Check ineligible and continue*) Ineligible

4. Does the volunteer appear cognitively functioning and able to understand the assent/consent process?
 Yes
 No (*Check ineligible and continue*) Ineligible

5. Does the volunteer appear visibly distraught or emotionally unstable (i.e. suicidal, manic, exhibiting violent behavior)?
 Yes (*Check ineligible and continue*) Ineligibl
eNo

6. Does the volunteer appear intoxicated or under the influence of psychoactive agents?
Yes (*Check ineligible*)
 Ineligible
 No

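### Some participants meet the viral-suppression primary outcome at entry, and the 3-month comparison neither adjusts for nor reports by baseline outcome status

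*Combined protocol and SAP*

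**What the plan says.** Criterion 3 of Study Inclusion (Aim 1) is an either/or rule: participants must "have a viral load ≥ 200 c/mL and/or report poor adherence (<90% of pills taken in the last 30 days". Outcome definitions uses the same cut-offs from the other side: "VL < 200 copies/mL will be considered virally suppressed", and "Medication adherence: greater than or equal to 90% on self-reported visual analog scaler".

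The Sampling section sets out both routes. For viral load: "Patients who are viremic and meet criteria 1-3 (HIV status, age) will be considered eligible for study inclusion", with no adherence condition. For adherence: "those who are virally suppressed will be queried about medication adherence (if <90% of pills taken in the past 30 days". Recruiting suppressed patients is thus deliberate.

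Appendix C, item 13, applies a missed-dose rule with no exception for viral load: "If a) is 1 or less AND b) is less than 3, check ineligible", where a) is doses missed in the past 7 days and b) is doses missed in the last month.

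Research Design describes the primary analysis as "comparing the primary outcomes (i.e., ART adherence and viral load suppression) of the intervention arm to the comparison arm at 3-months post initiation". Data Analysis Plan and Variables fits generalized linear models to that comparison. It names sociodemographic characteristics and urban or rural location as possible confounders or effect modifiers, and does not name baseline outcome status as a covariate, stratum or subgroup. The Study participation summary places clinic randomization before enrolment and the baseline survey.

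**The concern.** A participant who is suppressed at entry can only keep or lose the viral outcome; a viremic participant can only gain it or fail to. One between-arm difference in the proportion suppressed averages two distinct effects, weighted by the mix that the clinics happen to enrol. The plan neither fixes nor caps that mix.

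Two things are at stake. First, interpretation: a small overall difference could mean little effect on achieving suppression, or a useful effect there averaged with little effect in those already suppressed. Second, comparability: with 6 clinics per arm, and clinic staff enrolling after randomization, the share already suppressed may differ between arms. Baseline status is likely to be a strong predictor of the same outcome 3 months later, so an imbalance would move the estimate directly.

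**Working it through.** **The plan's own figure.** The sample size section assumes 6 sites per arm, 40 analysed per site, two measures per participant, and correlations of 0.05 within site and 0.2 within participant. The design effect is 1 + 2 × 39 × 0.05 + 0.2 = 5.10, so effective n per arm is 6 × 40 × 2 / 5.10 = 94.1. A two-sided 0.05 test gives power of 0.826 / 0.792 / 0.792 / 0.826 for 20 points, against 0.82 / 0.80 / 0.80 / 0.83 in Table 2. The table reproduces, but it concerns adherence. The plan states no target difference or power for viral suppression.

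**Share already suppressed.** Not given. A loose indication: a clinic needs at least 40 minority patients aged 16-35 with detectable virus and may enrol up to 50. At that minimum, enrolling all 40 leaves 10 of 50 places (20%); at the hypothesised 80% reach, 32 enrol and 18 of 50 (36%) remain. Other viremic patients could fill some of these places, so 20%, 40% and 60% below are assumptions.

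**Effect of an imbalance.** Assume that under control 30% of viremic and 85% of suppressed entrants are suppressed at 3 months. With share s suppressed at entry, the control rate is 0.30(1 − s) + 0.85s. At s = 0.30 it is 0.465 and at s = 0.40 it is 0.520. A 10-point arm difference in s thus gives 0.10 × 0.55 = 5.5 points with no treatment effect.

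**Mixing and power.** Further assume 50% suppression in viremic entrants under TXTXT and a gain of 0 to 5 points in suppressed entrants. Variance = [p0(1 − p0) + p1(1 − p1)] × (1 + 39 × 0.05)/40/6, with a t test on 10 df. The last column instead assumes 70% retention under control and a 20-point gain in suppressed entrants.

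| s | Difference, all enrolled | Power, all enrolled | Power, viremic only (20 points) | Power, all enrolled, 70% retention and 20-point gain |
|---|---|---|---|---|
| 0 | 20 | 0.67 | 0.67 | 0.67 |
| 20% | 16-17 | 0.46-0.51 | 0.64 | 0.65 |
| 40% | 12-14 | 0.29-0.38 | 0.59 | 0.66 |
| 60% | 8-11 | 0.17-0.28 | 0.51 | 0.69 |

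The viremic-only column uses 40(1 − s) per clinic. Which analysis has more power depends on what is assumed for suppressed entrants.

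**Gain from adjustment.** Replace the total variance by the within-stratum variance, keeping the same design effect.

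- s = 20%, no gain in suppressed entrants: total 0.41 × 0.59 + 0.57 × 0.43 = 0.487; within 0.8 × 0.46 + 0.2 × 0.255 = 0.419. Standard error ratio √(0.419/0.487) = 0.928, a reduction of 7%.
- s = 60%, 5-point gain: total 0.63 × 0.37 + 0.74 × 0.26 = 0.4255; within 0.4 × 0.46 + 0.6 × 0.2175 = 0.3145. Ratio 0.860, a reduction of 14%.

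**Adherence.** Criterion 3 and Sampling would admit a viremic patient reporting 90% or more. Item 13 would exclude most of these, though not all: 3 missed of 30 once-daily doses passes the screener and is 27/30 = 90%.

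**The case against.** The strongest reply is that the all-enrolled comparison answers the question the protocol asks. The background names sustaining suppression as well as achieving it, and Aim 1 concerns real-world effectiveness in poorly adherent youth. A suppressed patient who misses more than a tenth of doses is a target patient, and keeping such a patient suppressed is a benefit. This stands. It is why the primary population should not be replaced by those viremic at baseline: that would change the question, give the two primary outcomes different denominators, and define the subset by measurements made after clinics were randomized.

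A reader might also infer that criterion 3 cuts a planned 20-point viral effect. The documents do not support that: the 20 points concern adherence, and the viral inputs above are all assumed. Nor does the fall from about 0.80 in Table 2 to 0.67 in the first row come from criterion 3. It reflects the different outcome, a single measure and the t reference.

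The plan does say that models will account for repeated measures on individuals, so baseline may enter as a measurement. That could recover precision, but the text does not commit to it and would not yield separate results for achieving and maintaining.

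Finally, chance imbalance averages to zero over randomizations and forms part of the between-clinic variation. That is true, but it does not protect the single trial estimate, and it does not cover imbalance arising from enrolment after randomization.

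**Conclusion.** The point holds for viral suppression: the eligibility, sampling and outcome sections together ensure that any suppressed entrant meets a primary outcome on day 0, and the analysis section makes no provision for it. For adherence it holds only as far as the eligibility text, rather than item 13, governs entry; those passages conflict and must be reconciled. A reader might take the adherence overlap to be as large as the viral one, which the screener does not support.

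The entry rule alone does not bias the comparison, since it is the same in both arms. What it does is blend two effects in unknown proportion and leave the estimate exposed to arm imbalance: 0.55 points for each point of difference in the share suppressed, if the control rates are 30% and 85%. The power figures are illustrative and their ranking reverses under other plausible inputs, so they do not justify a restricted primary analysis. They do support adjusting for, and reporting by, baseline status.

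**What to change.** In Data Analysis Plan and Variables:

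- Keep the all-enrolled 3-month comparison as primary for both outcomes.
- Prespecify adjustment for baseline status on the same outcome: viral load below 200 or at least 200 copies/mL for suppression, and VAS below 90% or at least 90% for adherence.
- Prespecify the arm-by-baseline-status interaction, and report the 3-month effect separately for participants not at target at baseline (achieving) and at target (maintaining), with the number in each stratum by arm and clinic.
- State which viral load counts as baseline, because Sampling allows the screening value to be up to 12 months old.
- Reconcile criterion 3 and Sampling with Appendix C item 13.

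The cost is protocol and analysis-plan wording; baseline EMR data and the baseline survey are already collected. Adjustment should improve precision and guards against imbalance in baseline status, but does not itself remove the averaging of the two effects; the stratum estimates show that. With 12 clinics those estimates and the interaction will be imprecise, so they should be presented as supporting results with confidence intervals.

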Project staff will inform participants that they have the right to skip any questions that make them feel uncomfortable. Participants will be informed that participation is completely voluntary and that they are free to stop their involvement in the study at any time without any negative consequences. Participants can stop their text messages by replying "STOP" at any time or by calling the participating clinic to unenroll in the study. Participants will be informed of their rights to privacy and confidentiality and will be told that their answers to the survey (collected via computer-assisted self-interview [CASI]) will be kept confidential and not shared with others outside of the research staff. They will be informed that no information about them or provided by them during the research will be disclosed to others without their written permission, except if necessary to protect their rights or welfare (for example, if they are injured and need emergency care) or if required by law (i.e., child or elder abuse, harm to self or others).

Dependent on site randomization, intervention sites will sign up eligible participants to receive automated SMS messages from the DimagiCommCare platform. Participants will have the option to tailor the message content based on their own preferences and will be able to select to receive messages in English or in Spanish. The time the messages are delivered, and frequency will also be selected. Clinic staff will use the text message tailoring form to record tailored messages (Appendix D). Clinic staff will enter information from this form into the text messaging platform, and then test receipt of text messages by the participant before they complete this first intervention visit. If the participant chooses a text message that discloses their HIV status, clinic staff will guide participants into selecting a discrete message and discuss options for alternate text. Participants at control sites will receive standard of care adherence counseling but will not enroll in text messaging until their site is eligible to receive the intervention. Messages used previously include, "Have you taken your vitamins

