Retention will be facilitated through obtaining contact information for the participant during the initial stages of the enrollment process. To minimize participant and staff burden, the follow-up visits can be conducted virtually. Participants will be sent a personalized link to complete the follow-up survey via REDCap. Of note, there will not be financial reimbursement for participation in the

intervention as the goal of the project is to understand how TXTXT will work in the “real world” and inform wide scale routine implementation. Prior studies by Drs. [name], [name], and [name] with vulnerable adolescent and other marginalized populations have maintained >80% retention. We will employ best practices in participant retention including: 1) collecting extensive locator information (multiple addresses/emails, phone numbers, social media profile names, etc.); 2) identification and discussion of difficult-to-reach participants and potential solutions during weekly team meetings; and 3) maintaining flexibility with mode of follow-up (e.g., in person options as well as internet based). The investigative team and participating clinic staff will review the study team’s retention plans and will be asked for guidance on how to best keep YYALH engaged in the study for at least 6 months. No financial incentives will be provided to youth participating in the TXTXT intervention trial (Aim 1). At 3 months, 6 months, and 12 months post baseline, electronic medical record (EMR) data from participating clinics will be used to determine viral load; retention in care will be assessed for up to 12 months post baseline.

STUDY DESIGN AND DATA ANALYSIS

Study participation summary

1. 12 participating clinics randomized 1:1 into intervention or comparison arm
2. 50 participants at each clinic enrolled and complete baseline survey; baseline EMR data pulled
3. Participants at intervention clinics begin TXTXT after baseline survey and continue for 6 months
4. All participants complete a 3-month survey
5. Participants at comparison clinics begin TXTXT after 3-month survey and continue for 3 months
6. All participants complete a 6-month survey; 6-month EMR data pulled
7. TXTXT intervention stops at 6 months post baseline for all participants
8. 12-month EMR data pulled

Timepoint	Who	What	Data collected
zero	12 participating clinics	Randomized 1:1 intervention: comparison arm	

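### Enrolment follows clinic randomisation, recruiting staff know their clinic's arm, and no contact order or rule for filling the cap of 50 is stated, so the mix of entrants can differ by arm

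*Combined protocol and SAP*

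**What the plan says.** **Order of steps.** In the Study participation summary, item 1 is "12 participating clinics randomized 1:1 into intervention or comparison arm" and item 2 is "50 participants at each clinic enrolled and complete baseline survey; baseline EMR data pulled". The timepoint table agrees: randomisation is at time zero and participants appear at baseline.

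**Who recruits.** The Sampling section says: "We will ask each clinic to construct a list of potentially eligible patients and carefully track outreach, screening, and enrollment on an enrollment log provided". Viremic patients on the list "will be called by clinic staff to confirm eligibility and assess interest". Those who are suppressed or have no viral load are also to be contacted, to ask about adherence or about returning for laboratory tests. Under Procedures for Recruitment and Informed Consent (Aim 1), the clinic's own staff contact, screen, consent and enrol.

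**Knowledge of the arm.** The same section says: "Dependent on site randomization, intervention sites will sign up eligible participants to receive automated SMS messages". At intervention sites, staff set up and test the messages at the first visit.

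**Numbers.** "Clinics may enroll up to 50 participants". Clinic site inclusion criterion 1 begins "Clinic must have at minimum 40 current patients who are" and goes on to require racial/ethnic minority status, a detectable viral load and age 16-35.

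**Safeguards.** There is an enrollment log, and the list and eligibility assessments are reviewed weekly with each site. The stated purpose of that review is timely enrolment. Data Analysis Plan and Variables names sociodemographic characteristics and urban or rural location as possible confounders, to be selected on statistical significance and conceptual importance.

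**The concern.** Once a clinic is randomised, its staff know the arm of every patient they might call. Concealment at the time of recruitment is then lost unless the plan restores it, for example by fixing beforehand who is approached and in what order. It does not. The log records what happened, and the weekly review looks at pace.

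This matters because entry is by two routes with different prognoses. Study Inclusion admits a patient with viral load of at least 200 c/mL, or one who reports adherence below 90%, or both. A suppressed entrant already meets the viral-suppression outcome at baseline; a viremic entrant does not. If clinics in one arm fill their places mainly from one route and clinics in the other arm do not, the 3-month contrast mixes recruitment with the effect of TXTXT. With six clinics per arm, the habits of one or two can move an arm's mix. Part of any difference would lie in unrecorded traits, such as motivation or ease of contact, which later adjustment cannot reach. The trial is open and one primary outcome is self-reported.

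**Working it through.** **1. The plan's own power figure.** Inputs from Sample size, power calculation, and clinic scale up: 6 sites per arm, 40 analysed per site, 2 measures per participant, within-site correlation 0.05, within-participant correlation 0.2, type I error 0.05 (taken as two-sided).

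- Design effect = 1 + 2 × 39 × 0.05 + 1 × 0.2 = 5.10.
- Effective number per arm = 6 × 40 × 2 / 5.10 = 94.1.
- Power for 20 points at control rates 25/35/45/55% is 0.826/0.792/0.792/0.826, against the stated 0.82/0.80/0.80/0.83.
- Enrolment: 480 / 0.80 = 600, as stated.

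The power for 20 points and the enrolment total therefore reproduce. The point here is the order of steps, which changes neither.

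**2. What is fixed and what is open.**

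| Step | Stated in the plan | Not stated |
|---|---|---|
| Randomise clinics | First, at time zero | Whether the arm is withheld from recruiters |
| Build list | EMR query with defined criteria, done by the clinic | Date relative to randomisation; any lock |
| Contact | Viremic patients called; others contacted | Order, number of attempts |
| Enrol | Up to 50 | How the cap is filled when more are eligible |

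**3. Hypothetical size, viral suppression only, unadjusted.** The documents give no 3-month suppression rate by entry route and no expected imbalance, so both are assumptions.

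- Assumed 3-month suppression: suppressed entrants 80-85%, viremic entrants 35-50%. The gap between routes is then 30 points (80 − 50) to 50 points (85 − 35).
- Assumed difference between arms in the share of suppressed entrants: 10 to 20 points.
- False difference = mix difference × gap: 0.10 × 30 = 3; 0.10 × 50 = 5; 0.20 × 30 = 6; 0.20 × 50 = 10 points.

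Standard error of a single 3-month comparison, borrowing the plan's within-site correlation of 0.05 (given there for adherence):

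- Design effect = 1 + 39 × 0.05 = 2.95; participants per arm = 240.
- SE = √(2 p(1 − p) × 2.95 / 240), which is 7.5 points at p = 0.35 and 7.8 points at p = 0.45 or 0.55.

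Probability of a nominally significant result with no true effect = P(|Z + false difference/SE| > 1.96), by normal approximation:

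| False difference | SE 7.8 | SE 7.5 |
|---|---|---|
| 0 points | 5% | 5% |
| 3 points | 6.7% | 6.9% |
| 5 points | 9.8% | 10.3% |
| 6 points | 12.0% | 12.6% |
| 10 points | 24.9% | 26.7% |

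**The case against.** Several points on the other side are fair.

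- **List timing.** A reader might infer that lists are built only after randomisation. The documents do not say so: they date enrolment, not list construction, and criterion 1 implies that each clinic has counted its detectable patients before it qualifies. This stands. But nothing requires the list to be fixed early, and an undated list sets no order of contact.
- **Free choice of patients.** A reader might infer that staff pick whom they like. The query criteria are fixed and listed patients are to be contacted. The discretion lies in order, effort and the cap.
- **Participants' knowledge.** Staff know the arm, but volunteers may not: the Appendix C script speaks of texts as depending on a random choice still to come.
- **Room to select.** A clinic at the minimum has 40 detectable minority patients, fewer than the cap. If the 80% reach target were met with 50 enrolled, at most about 62 patients would be eligible (50 / 0.80 = 62.5), so most would be taken. But reach is a hypothesis, and suppressed and no-viral-load patients also belong on the list, so it can exceed 50.
- **Motive.** Comparison clinics give TXTXT after 3 months, and the screener requires text use in both arms. This weakens the incentive to select differently but does not remove it.
- **Adjustment.** The bias illustrated runs through baseline viral load, which is recorded. Adjusting for it would remove the illustrated bias under the model used. The analysis plan does not name that covariate, and the unrecorded part would remain.

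**Conclusion.** The weakness is real but narrower than it may appear. As written, the plan lets contact order and effort, and hence entry-route mix, depend on a known allocation. It does not show that this will happen.

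The size given is conditional: a false difference of 3-10 points in viral suppression, and a false-positive rate of about 12-27% for differences of 6-10 points. It rests on assumed route-specific rates, an assumed 10-20 point mix difference, the plan's within-site correlation and no baseline adjustment.

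A reader might set 10 points against the 20-point effect in the power section and conclude that half the target effect could be spurious. The documents do not support that: the 20 points refer to ART adherence, not viral suppression. For adherence even the direction may differ, since suppressed entrants must report adherence below 90% while viremic entrants may have any level. Bias through motivation or ease of contact is not quantified here.

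This is a cheap improvement to make before recruitment. Unrecorded selection cannot be repaired in the analysis afterwards.

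**What to change.** 1. Before the arm is disclosed to any clinic, each clinic runs the EMR query described under Sampling. It sends the study coordinator a coded list holding only a list number and viral-load stratum (viremic, suppressed, no viral load).
2. The coordinator date-stamps and locks the list and returns a computer-generated contact order, random within stratum. One pre-specified rule for moving between strata applies at every clinic, for example a fixed stratum sequence or fixed proportions. Random order within stratum alone would still let a clinic fill its places mainly from one route.
3. Clinics call in that order up to 50. Skips and out-of-order contacts are logged with reasons; patients identified later are appended and flagged.
4. Add baseline viral-load status (entry route) as a pre-specified covariate in the 3-month models under Data Analysis Plan and Variables.
5. Report numbers listed, contacted and enrolled by arm and stratum.
6. Amend Procedures for Recruitment and Informed Consent, the Study participation summary and Sampling to match, with the list lock placed before item 1 of the summary.

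**Cost.** A short protocol amendment. The query, log and coordinator already exist, and no extra patients are needed. The query is run slightly earlier, and clinics lose some freedom to approach whoever attends that day.
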